8.1.4 End of Treatment (EOT) Visit Schedule and Procedures

This visit will occur on the first outpatient visit following platelet count recovery (within one week) or within three days of count recovery in the inpatient setting. Procedures will include a verbal history of any bleeding or thrombotic symptoms, focused physical exam for evidence of either, FACT-Th18 questionnaire and results of the most recent complete blood count ordered by the patient's provider.

9.0 Subject Discontinuation of Active Treatment

Randomization may be broken and active treatment discontinued for any of the reasons outlined in section 7.7.1. Additionally, active treatment may be discontinued for any of the following reasons.

9.1 All reasons for discontinuation of treatment must be documented and the study team must be notified within 24 hours if a subject discontinues treatment. Reasons include:

9.1.1 Completion of protocol treatment.

9.1.2 Initiation of any malignancy-directed therapy other than that being given at the time of randomization

9.1.3 Withdrawal of consent; the patient may withdraw from the study at any time for any reason.

9.1.4 At investigator's discretion

9.1.5 Pregnancy

9.1.6 Grade 3 or 4 bleed (Appendix 3)

9.1.7 progressive or new VTE or ATE requiring change in antithrombotic management

9.2 For any reason other than withdrawal of consent, subjects will continue to be observed for the study period (until platelet count recovery or 30 days from randomization, whichever comes first). They will also have the same 30 day follow up (described in section 7.8) as patients who remain on active treatment.

10.0 Adverse Events

10.1 Expedited Reporting Requirements

In accordance with Fred Hutch/UW Cancer Consortium IRB policy, all adverse events (AEs; whether occurring on-site or off-site), which in the opinion of the principal investigator (PI) are (1) unexpected, and (2) related or possibly related to the research, and (3) serious or suggests

that the research places research participants or others at a greater risk of physical or psychological harm than was previously known or recognized, will be submitted to the IRB within ten (10) calendar days of learning of the problem. Both the “Expedited Reporting Form for Unanticipated Problems or Noncompliance” and the “Adverse Event Reporting Form”, or equivalent forms, will be completed for this reporting.

10.2 Definitions

10.2.1 Adverse Event (AE): Any harm or untoward medical occurrence in a research participant administered a medical product, medical treatment or procedure even if it does not necessarily have a causal relationship with the product, treatment, or procedure. An adverse event can be any unfavorable and unintended sign (including an abnormal laboratory finding, for example), symptom, or disease temporally associated with the use of a medical product, medical treatment, or procedure whether or not considered to be related. Mechanisms of obtaining information on AE include study visits, hospital progress and discharge notes.

10.2.2 Related or Possibly Related AE: An AE is “related or possibly related to the research procedures” if in the opinion of the principal investigator, it was more likely than not caused by the research procedures. AEs that are solely caused by an underlying disease, disorder or condition of the subject or by other circumstances unrelated to either the research or any underlying disease, disorder or condition of the subject are not “related or possibly related”. If there is any question whether or not an AE is related or possibly related, the AE should be reported.

10.2.3 Serious AE (SAE): An adverse event that results in any of the following outcomes:

- Death
- Life-threatening adverse event (real risk of dying)
- Prolongation of hospitalization*
- Persistent or significant disability/incapacity/or change in psychosocial status
- Congenital anomaly
- Requirement of intervention to prevent permanent impairment or damage

*Hospitalization itself will not be considered a serious adverse event if required for complications or treatment of the underlying hematologic malignancy, treatment or comorbid conditions. Hospitalization will be considered a SAE if it fulfills the criteria for a serious and unexpected adverse event as otherwise described.

10.2.4 Unexpected AE: An unexpected adverse event is defined as an event that has a nature or severity, or frequency that is not consistent with the applicable investigator brochure, or the prior medical condition of the subject or other treatment given to the subject. “Unexpected,” as defined in this study, refers to an adverse experience that has not been previously observed and reported in patients requiring anticoagulation and/or experiencing thrombocytopenia.

10.3 Grading Adverse Event Severity

All bleeding will be graded in severity according to the WHO criteria (Appendix 3). All other (unexpected) AEs will be graded in severity according to the NCI Common Terminology Criteria for Adverse Events (CTCAE) Version 4.0 (<http://ctep.cancer.gov>). If a CTCAE criterion does not exist, the investigator should use the grade or adjectives: Grade 1 (mild), Grade 2 (moderate),

Grade 3 (severe), Grade 4 (life-threatening), or Grade 5 (fatal) to describe the maximum intensity of the adverse event.

10.4 Monitoring, Recordings, and Standard Reporting of Adverse Events

Only grade ≥ 2 adverse events will be recorded, graded, and reported as appropriate per 10.1. Grade ≤ 3 heme AEs are anticipated for all subjects based upon inclusion criteria, are not anticipated to be related to study procedures and will not be reported. Grade 4 heme AEs will be reported, however. AEs will be collected for the duration that the patient remains on protocol. If a subject decides to terminate the study early or breaks randomization or any of the reasons described in 7.7.1 their medical record will continue to be followed for AEs for the study period as defined in 7.6. AEs that do not meet the requirement for expedited reporting will be reported to the IRB as part of the annual renewal of the protocol.

10.5 Adverse Event Recording Period

AEs will be monitored and recorded in the study database from the first time the subject is simultaneously (1) randomized to a transfusion threshold and (2) experiences a platelet count $< 50 \times 10^9/L$ to the end of the study period. AEs with an onset date prior to the first day of the study period will not be recorded, except in the case of clinically significant worsening of the AE during the specified AE monitoring time frame.

11.0 Data and Safety Monitoring Plan

Institutional support of trial monitoring will be in accordance with the Fred Hutch/University of Washington Cancer Consortium Institutional Data and Safety Monitoring Plan. Under the provisions of this plan, Fred Hutch Clinical Research Support (CRS) coordinates data and compliance monitoring conducted by consultants, contract research organizations, or Fred Hutch employees unaffiliated with the conduct of the study. Independent monitoring visits occur at specified intervals determined by the assessed risk level of the study and the findings of previous visits per the institutional DSMP.

In addition, protocols are reviewed at least annually and as needed by the Consortium Data and Safety Monitoring Committee (DSMC), Fred Hutch Scientific Review Committee (SRC) and the Fred Hutch /University of Washington Cancer Consortium Institutional Review Board (IRB). The review committees evaluate accrual, adverse events, stopping rules, and adherence to the applicable data and safety monitoring plan for studies actively enrolling or treating subjects. The IRB reviews the study progress and safety information to assess continued acceptability of the risk-benefit ratio for human subjects. Approval of committees as applicable is necessary to continue the study.

The trial will comply with the standard guidelines set forth by these regulatory committees and other institutional, state and federal guidelines.

12.0 Data Management/Confidentiality

Research data will be recorded in a study-specific, password protected database using a unique study ID for each patient to assure patient confidentiality. Data from source documents will be transcribed into this database. Source documents are documents where patient data are recorded and documented for the first time. They include, but are not limited to, hospital

records, clinical and office charts, laboratory notes, memoranda, quality of life assessments, pharmacy dispensing records, recorded data from automated instruments, copies of transcriptions that are certified after verification as being accurate and complete, X-rays, patient files, and records kept at the pharmacy, laboratories, and medico-technical departments involved in the clinical trial. There will be no case reports forms (CRFs) used for this trial.

The investigator will ensure that data collected conform to all established guidelines. Each subject is assigned a unique subject number to protect subject confidentiality. Subjects will not be referred to by this number, by name, or by any other individual identifier in any publication or external presentation. The licensed medical records department, affiliated with the institution where the subject receives medical care, maintains all original inpatient and outpatient chart documents. Patient research files will be maintained under control of the Principal Investigator and/or study team and kept in a locked office or file room within a secure building. Access to the study database will be restricted by electronic password protection and restricted access to computers (i.e., locked offices).

13.0 Statistical Considerations

13.1 Study Design

This is a pilot study of two different platelet transfusion thresholds in patients receiving anticoagulation during periods of thrombocytopenia related to the treatment of hematologic malignancies. Patients will be randomized to transfusion thresholds in a 1:1 fashion.

13.2 Primary/Secondary Endpoints/Hypotheses and Analytical Methods

The primary endpoints of this study are (1) enrollment and (2) compliance. Enrollment will be described at the end of a 12-month period and (2) compliance will be evaluated as described in section 3.3.1. The secondary endpoints described in sections 3.3.2 will also be reported and analyzed with descriptive statistics only. This trial is not powered to detect statistically significant differences between the study arms for these clinically important endpoints. Rather, the primary goal is to establish feasibility for enrollment into a formal trial.

13.2 Sample Size and Power

As this study is purely descriptive, it will not be powered to determine efficacy or safety of either intervention. The sample size has been chosen based upon the rate of enrollment necessary to establish the feasibility of an appropriately powered study.

A full trial would be a non-inferiority study powered for safety. The primary outcome would be WHO Grade 2 or above bleeding and the study would be powered to identify a relative risk of 1.4 or greater. This is based upon trials of anticoagulation, in which RR of 1.4 for bleeding is standardly considered to be acceptable.

Based on historical data, we assume a bleeding rate of $\geq 40\%$ at the higher threshold. A relative risk of 1.4 would correspond to an assumed-true bleeding rate at the lower threshold of 56% ($.56/.40 = 1.4$). If we assume that the true bleeding rate at the lower threshold is also 40% , then with 125 patients per treatment arm, we'll have approximately 84% power to deem the lower threshold non-inferior to the higher threshold (at the one-sided significance level of $.05$).

In other words, if the assumed-true bleeding rates in each arm are 40%, then the upper limit to the 95% confidence limit for the difference between the estimate bleed rates (bleed rate at lower threshold – bleed rate at higher threshold) is below 0.16 with a probability of 0.84. If we assume a true bleeding rate of 60% at the higher threshold, then a relative risk of 1.4 (or less) corresponds to an assumed-true rate in the lower threshold of 84% (or less). If the assumed-true bleeding rates in both arms is 60%, then 125 patients/arm yield approximately 99% power to deem the lower threshold as non-inferior (as defined above).

Anticipating a two-year enrollment period across fifteen sites, expecting that other sites will enroll at a slightly lower rate than the primary site randomization of 12 patients in a one-year period at our Center will be a rough benchmark for feasibility (although other factors will be considered when judging this approach as feasible for purposes of designing the randomized Phase III trial, including compliance with the study protocol and event rate).

13.3 Ethnic and Gender Distribution Chart

TARGETED / PLANNED ENROLLMENT: Number of Subjects			
Ethnic Category	Sex / Gender		
	Females	Males	Total
Hispanic or Latino	0	0	0
Not Hispanic or Latino	5	7	12
Ethnic Category Total of All Subjects	5	7	12
Racial Categories			
American Indian / Alaska Native	0	0	0
Asian	0	0	0
Native Hawaiian or Other Pacific Islander	0	0	0
Black or African American	0	0	0
White	5	7	12
Racial Categories: Total of All Subjects	5	7	12

14.0 Investigator Obligations

The PI is responsible for the conduct of the clinical trial at the site and is responsible for personally overseeing the treatment of all study subjects. The PI must assure that all study site personnel, including sub-Investigators and other study staff members, adhere to the study protocol and to all applicable regulations and guidelines regarding clinical trials both during and after study completion.

All subjects are informed of the nature of the program, its possible hazards, and their right to withdraw at any time, and each subject signs a form indicating their consent to participate prior to receiving any study-related procedures.

15.0 Administrative and Regulatory Considerations

15.1 Protocol Interpretation and Compliance

The procedures defined in the protocol are carefully reviewed by the PI and his/her staff prior to the time of study initiation to ensure accurate representation and implementation. Protocol

amendments, if any, are reviewed and implemented promptly following IRB/EC and relevant Competent Authorities approval.

15.2 Ethical Considerations

The Investigator agrees to conduct this study in accordance with applicable United States FDA clinical trial regulations and guidelines, the ICH (E6) GCP guidelines, the IRB/EC and local legal requirements and with the Declaration of Helsinki (1989). The Investigator will conduct all aspects of this study in accordance with all national, state, and local laws of the applicable regulatory agencies.

15.3 Informed Consent

The PI and qualified designees assume the responsibility of obtaining written Informed Consent for each subject or the subject's legally authorized representative before any study-specific procedures are performed.

Subjects meeting the criteria set forth in the protocol will be offered the opportunity to participate in the study. To avoid introduction of bias, the Investigator must exercise no selectivity with regard to offering eligible subjects the opportunity to participate in the study. All candidate subjects will receive a comprehensive explanation of the proposed treatment, including the nature of the therapy, alternative therapies available and other factors that are part of obtaining a proper Informed Consent. Subjects will be given the opportunity to ask questions concerning the study, and adequate time to consider their decision to or not to participate. Informed Consent will be documented by the use of a written Consent Form that includes all the elements required by ICH guidelines. The form is to be signed and dated by the subject or subject's legally authorized representative and by the person who administers the consent process. A copy of the signed form will be given to the person who signed it and the original signed Consent Form will be maintained with the subject's study records. If an amendment to the protocol changes the subject participation schedule in scope or activity, or increases the potential risk to the subject, the Informed Consent Form must be amended. Any amended Informed Consent must be reviewed by the Sponsor or designee and approved by the IRB/EC prior to use. The revised Informed Consent Form must be used to obtain re-consent from any subjects currently enrolled in the study if the subject is affected by the amendment, and must be used to document consent from any new subjects enrolled after the approval date of the amendment.

15.4 Institutional Review Board/Ethics Committee

The PI will assure that an appropriately constituted IRB/EC that complies with the requirements of 21 CFR Section 56 or written assurance of compliance with ICH (E6) guidelines will be responsible for the initial and continuing review and approval of the clinical study. Before initiation of the study, the PI or designee will forward copies of the protocol and Consent Form to be used for the study to the IRB/EC for its review and approval. The PI or designee will also assure that all changes in the research activity and all unanticipated problems involving risks to human subjects or others will be reported promptly to the IRB/EC, and that no changes will be made to the protocol without prior IRB/EC approval, except where necessary to eliminate apparent immediate hazards to human subjects. The Investigator or designee will be responsible for submitting periodic progress reports to the IRB/EC at intervals appropriate to

the degree of subject risk involved in the study, but not less than once per year and at the completion or termination of the study.

16.0 Stopping the Study

[figure not shown]
The investigators may decide to stop the study at any point, for any reason. The following reasons will lead to premature termination of the trial

- WHO grade 3/4 bleeding rate <30% in the lower transfusion threshold arm following enrollment of 8 patients

References

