**FRED HUTCHINSON CANCER RESEARCH CENTER
UNIVERSITY OF WASHINGTON SCHOOL OF MEDICINE**

Current version: 3

Previous version:2

**Management of Venous Thromboembolic Events (VTE) in Patients
with Hematologic Disorders and Treatment-Induced
Thrombocytopenia: a Pilot Study**

Principal Investigator:

- [name], Professor, UW [contact])

Co-Investigators at FHCRC/UW

- [name] PhD, Assistant Member, FHCRC, Professor, UW [contact])
- [name], Professor, UW [contact])

Study Coordinator FHCRC:

- [name], Clinical Research Coordinator SCCA [contact]);
email:[contact]

Data Coordinator FHCRC:

- [name], Clinical Research Coordinator,, SCCA [contact]); email:
[contact]

Emergency Phone (24 hours):

For non-transplant patients: Call the paging operator at the University of Washington Medical Center at [contact], and ask for the Fellow on call for Hematology/Oncology.

For transplant patients: Call the 8NE front desk at the University of Washington Medical Center at [contact], and ask for the triaging provider covering the transplant service.

PROTOCOL SYNOPSIS

Protocol Title	Management of Venous Thromboembolic Events (VTE) in Patients with Hematologic Disorders and Treatment-Induced Thrombocytopenia: a Pilot Study
Protocol Number	
Protocol Sponsor	None
Trial Phase	Pilot
Trial Type	Noninferiority
Clinical Indication	Management of treatment-induced thrombocytopenia during anticoagulation
Study Objectives	
 1) Determine feasibility of an RCT comparing platelet transfusion thresholds of 30×10^9 vs 50×10^9 in anticoagulated patients 2) Report bleeding outcomes as they would be in a full trial 3) Report patient reported outcomes as they would be in a full trial
Study Design	Randomized controlled trial
Population	Adult patients with moderate to severe thrombocytopenia related to the treatment of a hematologic malignancy and/or stem cell transplant for a hematologic disorder who require anticoagulation for a recently diagnosed venous thrombosis.
Primary Endpoints	(1) Feasibility defined as ≥ 12 patients enrolled over a 1-year period and (2) $\geq 70\%$ compliance with study-determined transfusion threshold at the time of count recovery

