2.1 Background and Rationale

Venous thromboembolic disease (VTE) is a common complication of hematologic malignancy. The prolonged periods of thrombocytopenia experienced by these patients during curative-intent chemotherapy and/or hematopoietic stem cell transplant (HSCT) do not appear to provide protection against VTE: the rate of symptomatic VTE may be as high as 5% by day 180 post HSCT.¹ Data to guide management of thrombosis in these patients, particularly during periods of moderate to severe thrombocytopenia, are sparse.

The International Society on Thrombosis and Haemostasis (ISTH) has suggested an empirical cut-off of $50 \times 10^9/L$ as the minimum platelet threshold above which therapeutic anticoagulation is considered to be safe. Accordingly, a recommendation has been made to consider platelet

transfusion support to maintain a platelet count above this threshold if therapeutic anticoagulation is warranted, as in the setting of acute VTE.² These recommendations, however, have been made on the basis of expert consensus, as there is no high-quality evidence.

The only data currently available in the literature comes from very small retrospective studies and case series. These suggest the risk of bleeding (WHO grade 2 or greater) among patients with moderate to severe thrombocytopenia is relatively low (between 7.7 and 9.4% over a 3-6 month period) when patients are initiated on anticoagulation and then transfused toward a goal of $40\text{-}50 \times 10^9/\text{L}$.^{3,4} Approximately half of these bleeding episodes represent major bleeding (3.8% of patients).⁴

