2.2 Clinical Data to Date

A recent survey of malignant/nonmalignant hematologists and transfusion medicine experts about this topic found a marked degree of variation in proposed transfusion thresholds (ranging from 25 to $50 \times 10^9/\text{L}$).⁵ A recent retrospective study of eighty-two SCCA patients with VTE during a period of treatment-related thrombocytopenia demonstrated that most providers here manage VTE with therapeutic anticoagulation, adjusting the platelet transfusion goal to $50 \times 10^9/\text{L}$, often resulting in two or more weeks of frequent platelet transfusions, potentially repeated in future treatment cycles. Bleeding rates (WHO grade 2 or above) were noted to be somewhat higher than those previously reported in the literature (37% at 30 days), but comparable to or less than rates expected in patients with severe treatment related thrombocytopenia (transfusion threshold $10 \times 10^9/\text{L}$), which is as high as 70% over a period of 30 days or less.⁶ While retrospective assessments of bleeding, particularly grade 2 bleeds, are limited and some bleeds are likely missed by this method, we expect this rate of bleeding is more representative of actual outcomes than those previously reported in the literature.

Our retrospective review demonstrated that the vast majority of patients at our institution in this situation are transfused to maintain a platelet count $\geq 50 \times 10^9/\text{L}$, with the above noted bleeding rate. The majority of bleeds occurred during a time when the platelet count was at or above this goal (mean $52 \times 10^9/\text{L}$) although the retrospective nature made it impossible to define or compare 'at risk' times. We did, however, note a number of transfusion related complications with this strategy including transfusion reactions in 13% of patients and volume overload requiring diuretic therapy or dialysis in 37% of patients.

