2.4 Risks/Benefits

The primary risk of a decreased platelet transfusion threshold would be that of increased bleeding rates. Platelet-type, or bleeding due to defects of primary hemostasis, tends to be primarily mucocutaneous, including epistaxis, gum bleeding and menorrhagia,¹⁰ rather than into soft tissue, joints or body cavities as with disorders of secondary hemostasis (clotting factor deficiencies, including those induced by anticoagulation). Thrombocytopenic bleeding in the unanticoagulated population is largely low grade (WHO grade 2 or less) and rarely requires intervention beyond platelet transfusion.^{6,11}

Potential benefits of a decreased platelet transfusion threshold are numerous. Objective benefits to the individual patient might include decreased rates of transfusion-related complications, including transfusion reactions, infections, volume overload and alloimmunization. Subjective benefits of decreased transfusion frequency/requirement might include improved sense of well-being and quality of life, particularly for outpatients who may require fewer trips for medical care and benefit from increased time at home. Systemic benefits might include decreased overall cost of care and decreased drain on resources, of particular importance when blood products are in short supply.

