4.0 SAFETY CONSIDERATIONS

4.1 Stopping Rules

The study will be stopped early if major bleeding (WHO grade 3 or greater) is noted in 3 or more patients on the experimental arm once eight patients have been enrolled (and at least four randomized to the experimental arm).

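### Section 16.0 ends the trial when major bleeding on the lower-threshold arm is below 30%, the opposite of Section 4.1, and reversing the sign alone would not make the two rules agree

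*Combined protocol and SAP*

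**What the plan says.** Section 16.0 (Stopping the Study) introduces its list with "The following reasons will lead to premature termination of the trial". The only item is "WHO grade 3/4 bleeding rate <30% in the lower transfusion threshold arm following enrollment of 8 patients".

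Section 4.1 (Stopping Rules) stops the study early if "major bleeding (WHO grade 3 or greater) is noted in 3 or more patients on the experimental arm", once eight patients are enrolled and with "at least four randomized to the experimental arm".

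Section 2.4 gives the direction of the safety concern: "The primary risk of a decreased platelet transfusion threshold would be that of increased bleeding rates".

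The experimental arm is the lower-threshold arm (Section 2.3). The WHO scale in Appendix 3 ends at grade 4, so the two descriptions of major bleeding cover the same events. Allocation is 1:1 (Section 13.1) and about 12 patients are planned (Section 2.0).

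**The concern.** The two rules share the arm, the event and the enrolment point, and both are mandatory, but they point in opposite directions. No section describes Section 16.0 as a futility rule or gives a reason to stop for low bleeding.

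Section 11.0 has the review committees evaluate the stopping rules. From the eighth enrolment they would hold two conflicting instructions. If Section 16.0 were applied as printed, a low bleeding count would close the pilot at eight patients. The Synopsis defines enrolment feasibility as at least 12 "patients enrolled over a 1-year period", so that primary endpoint could not be met.

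The rules also differ in form. Section 4.1 uses a count with a minimum arm size; Section 16.0 uses a proportion with none. Correcting the sign would leave that difference in place.

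**Working it through.** The documents give no operating characteristics for either rule, so there is no stated figure to reproduce.

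**Inputs.** Let X be the number of patients with a major bleed among n on the lower-threshold arm, X ~ Binomial(n, p), with complete observation when eight are enrolled. Under 1:1 allocation n is about 4 at that point. The true rate p is assumed:
- 3.8% is the only major-bleed rate in the documents (Section 2.1: retrospective, 3-6 months, transfusion goal 40-50 × 10⁹/L).
- 18.5% is half of the institution's 37% rate of grade 2 or higher bleeding at 30 days (Section 2.2). It borrows the one-half ratio of Section 2.1, which comes from a different series.
- 10%, 20%, 30% and 50% span a range.

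**Step 1: both rules as printed.**

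| n on arm | Section 16.0 stops at X | Section 4.1 stops at X | Trial continues at X |
|---|---|---|---|
| 4, 5 or 6 | 0 or 1 | 3 or more | 2 only |
| 7 or 8 | 0, 1 or 2 | 3 or more | none |

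**Step 2: probability that Section 16.0, as printed, ends the trial.** For n = 4 and 5 this is P(X ≤ 1) = (1−p)ⁿ + n·p·(1−p)ⁿ⁻¹. Example, n = 4, p = 0.20: 0.8⁴ + 4 × 0.2 × 0.8³ = 0.4096 + 0.4096 = 0.819.

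| p | n = 4 | n = 5 |
|---|---|---|
| 3.8% | 0.992 | 0.987 |
| 10% | 0.948 | 0.919 |
| 18.5% | 0.842 | 0.768 |
| 20% | 0.819 | 0.737 |
| 30% | 0.652 | 0.528 |

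At p = 50% and n = 4 it is still 0.313.

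**Step 3: reverse only the sign (stop if X/n > 0.30).** Two bleeds give 2/4 = 50%, 2/5 = 40%, 2/6 = 33%, 2/7 = 29% and 2/8 = 25%. The reversed rule therefore stops at 2 for n = 4, 5 or 6, where Section 4.1 needs 3. The two agree at n = 7 or 8. Exactly 30% cannot occur for n = 3 to 8, so > and ≥ give the same result.

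Stopping probabilities at p = 30%:

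| n | Reversed Section 16.0, P(X ≥ 2) | Section 4.1, P(X ≥ 3) |
|---|---|---|
| 4 | 0.348 | 0.084 |
| 5 | 0.472 | 0.163 |
| 6 | 0.580 | 0.256 |

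For n = 4: 1 − 0.652 = 0.348, and 4 × 0.3³ × 0.7 + 0.3⁴ = 0.0756 + 0.0081 = 0.084.

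**Step 4: minimum arm size.** With n = 3, one bleed is 33%. The reversed rule would stop with probability 1 − 0.9³ = 0.271 at p = 10% and 1 − 0.8³ = 0.488 at p = 20%. Section 4.1 is not active until a fourth patient is on the arm.

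The chance of fewer than four of the first eight on the arm depends on the randomisation method, which is not stated:
- Simple 1:1: (1 + 8 + 28 + 56)/256 = 93/256 = 0.363.
- Permuted blocks of 2, 4 or 8: 0.
- Permuted blocks of 6: three of the first six are on the arm, and neither of the next two is with probability (3/6) × (2/5) = 0.20.

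**The case against.** **The sign is an obvious slip.** Nobody would end a safety-minded pilot because bleeding was low, committee review makes unnoticed literal use unlikely, and Section 4.1 still provides a stop for harm. Most of this stands. The probabilities in Step 2 apply only to the literal reading, and harm protection is not lost once four patients are on the arm. But Section 15.4 bars changes to the protocol without prior IRB approval except for immediate hazards, so staff may not simply read the sign the other way.

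**The point turns on one character in text extracted from a PDF.** The sign should be checked against the source page. Comparison signs elsewhere in the text read sensibly, and Steps 3 and 4 apply even if the page shows the opposite sign.

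**Two harm rules can coexist.** With the sign reversed, the study could stop when either is met, and Section 16.0 already lets the investigators stop at any time. That is workable, but the protocol does not say so, and Section 4.1 would then have no effect at n = 4 to 6 because the other rule always acts first.

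**The rules need not mean a single look at eight patients.** This is fair. Both can be read as remaining in force after the eighth enrolment, so the probabilities describe one evaluation at that point and not the whole trial.

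**Eight patients in Section 16.0 could mean eight on the arm.** The reversed rule would then need 3 of 8 and match Section 4.1. That reading is strained with about 12 patients at 1:1, and it leaves the opposite direction as printed untouched.

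**Conclusion.** The concern holds with high confidence and needs correction. Sections 4.1 and 16.0 give opposite mandatory instructions for the same arm, event and enrolment point; this rests on the text and needs no assumption. The boundary difference after a sign change (two bleeds against three at four to six on the arm) and the difference in minimum arm size are plain arithmetic.

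The probabilities are illustrations. They assume the bleed rates shown and one fully observed evaluation at eight enrolled; the 36% chance of fewer than four on the arm holds only for simple randomisation. The practical damage is a contradictory instruction and, if followed literally, a very likely false stop at low bleeding rates. It is not a loss of all protection against harm.

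**What to change.** Amend Sections 4.1 and 16.0 so that one stopping rule is stated once, with a cross-reference from the other section. The rule should settle:

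- the direction;
- whether it is a count or a rate;
- the boundary;
- the denominator, and whether eight means patients enrolled in total or on the arm;
- the minimum number on the lower-threshold arm;
- whether it is applied once or stays in force to the end of enrolment.

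The boundary is for the investigators and the DSMC to choose; a table of stopping probabilities like those above would help them. The cost is a short protocol amendment with IRB approval, with no additional patients and no new data.
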